7.1.6.1 Hematology

Blood draws for hematology will include:

- Hemoglobin, hematocrit, erythrocytes, reticulocytes, mean cell hemoglobin (MCH), mean corpuscular volume (MCV), mean corpuscular hemoglobin concentration (MCHC), platelet count, white blood cell count with differential.

7.1.6.2 Coagulation

Blood draws for coagulation will include:

- Prothrombin time (PT), international normalized ratio (INR), activated partial thromboplastin (aPTT)

7.1.6.3 Chemistry

Blood draws for chemistry will be performed per the Schedule of Assessments (Table 6-1). Analysis will vary based visit day as follows:

- **Full serum chemistry**
AST, ALT, alkaline phosphatase (ALP), gamma glutamyl transferase (GGT), total bilirubin (TBIL), direct and indirect bilirubin, creatine phosphokinase (CPK), lactate, bicarbonate, uric acid, creatinine, urea (BUN), estimated glomerular filtration rate (eGFR), sodium, potassium, calcium, inorganic phosphate, chloride, albumin, total protein, glucose (fasting), glycated hemoglobin A1C (HbA1C), high sensitivity C-reactive protein (hsCRP) and tryptase (as required)
- **Limited serum chemistry**
ONLY: AST, ALT, ALP, GGT, TBIL, CPK, creatinine, eGFR, HbA1C and tryptase (as required)

7.1.6.4 Urinalysis

Urinalysis will be performed at the time points defined in the Schedule of Assessments (Table 6-1) and evaluated by dipstick analyses at the investigational site (a standardized dipstick test will be supplied by the central laboratory). Urinalysis will be performed from a sample of mid-stream urine. In case of abnormal results, microscopy and other assessments will be performed at the local laboratory and the abnormality recorded as an AE.

The following parameters will be assessed:

- Nitrite, protein, glucose, ketone, urobilinogen, bilirubin, red blood cells/erythrocytes, white blood cells/leukocytes, pH, urine sediment (microscopic examination will be only performed in the event of abnormalities)

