6.1 Schedule of Events/Assessments

The schedule of assessments is provided in [Table 6-1](#).

If the COVID-19 pandemic limits or prevents on-site study visits, alternative methods of providing continuing care may be implemented. Phone calls or remote/virtual contacts (e.g. teleconsult) can replace on-site study visits, for the duration of the pandemic until it is safe for the participant to visit the site again. Also, the visits window has been extended to +/-2 months during the pandemic.

Table 6-1 Schedule of Assessments

Study Day Visit window (± days)	Study Entry/ Double blind treatment	Open Label Treatment Phase		EOS ¹
	Day 1 ² (N/A)	Day 90 (First Dose) (±30)	Subsequent dosing visits ³ (i.e. Days 270, 450, 630, 810, 990) (±30)	Final Follow-up Day 1080 (≥ 90 days post final dose)
Informed consent	x			
Inclusion/exclusion Criteria	x			
Physical examination				x
Vital signs ⁴		x	x	x
Full serum chemistry ⁵				x
Limited serum chemistry ⁵		x	x	
Hematology and coagulation ⁶				x
Urinalysis (local) ⁷				x
Pregnancy test (local) ⁸		x	x	x
Lipids and lipoproteins		x	x	x
Double blinded inclisiran or placebo ^{10, 11}	x			
Open label Inclisiran administration ¹¹		x	x	
Concomitant medications ¹²		x	x	x
AE/SAE reporting ¹²		x	x	x
Drug and device deficiencies (including AE/SAEs related to the drug or device deficiency)	x	x	x	x

AE = adverse event; EOS = end of study; SAE = serious adverse event

1. EOS visit should occur at least 90 days following the last inclisiran dose once a decision is made to end the study (either by the subject, investigator or sponsor). For subjects prematurely and permanently discontinued from study treatment, who are not willing to return within the 90 day timeframe, the EOS visit will be scheduled as soon as possible, or if decision to discontinue and not return is made at a specific visit, this visit will become the EOS visit and EOS visit procedures should be followed.

2. Day 1 visit is the same as EOS visit in the previous qualifying ORION study. Aside from informed consent and eligibility, procedures will not be repeated but will be those captured during feeder study EOS visit except for subjects enrolled in Sweden. See Section 3.1 and Section 6.3 Sweden Specific Protocol Amendment 1 (to Global Amendment 1 version), dated 1 Nov 2018.

3. Dosing visits will occur every 180 days until the study ends for each respective subject. Visit windows have been extended to +/-2 months due to COVID-19.

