6.3 Study Entry/Double-blind Treatment phase (Day 1)

The following procedures and laboratory assessments are conducted as part of the EOS visit from the feeder study and are not repeated for Day 1 of this trial. The same values/samples data will be used for Day 1 assessments in ORION-8 were applicable except for subjects enrolled in Sweden. Sweden Specific Protocol Amendment 1 (to Global Amendment 1 version, dated 1 Nov 2018) was implemented to allow limited lab tests to be done on Day 1 and to collect any safety information during the gap between feeder's EOS and Day 1 of this study until ethics committee approval was granted in that country

- Physical examination
- Vital signs (blood pressure and heart rate)
- Central clinical laboratory (full serum chemistry, hematology and coagulation) ([Section 7.1.6](#))
- Urinalysis (performed locally, using central laboratory supplies) ([Section 7.1.6.4](#))
- Pregnancy test (performed locally, using central laboratory supplies) (women of childbearing potential only) (results of test must be reviewed prior to dosing)
- Fasting lipid and lipoprotein profile ([Section 7.2](#))

-  Concomitant medication assessment (relevant ongoing concomitant medications from feeder study are reported at this visit)
- AE/SAE reporting (ongoing AEs/SAEs from feeder study are reported at this visit)

The following ORION-8 specific procedures will be performed on Day 1:

- Informed consent for the ORION-8 study
- Assessment of inclusion and exclusion criteria
- Administration of double-blinded placebo or inclisiran treatment (except for subjects moving over from ORION-3)

The following additional procedures were performed on Day 1 for subjects in Sweden only and data used for Day 1 assessments (the feeder study EOS data was not used for the following assessments):

- Central clinical laboratory (limited chemistry, hematology (no coagulation) ([Section 7.1.6](#))
- Pregnancy test (performed locally, using central laboratory supplies) (women of childbearing potential only) (results of test must be reviewed prior to dosing)

- Fasting lipid, lipoprotein profile and PCSK9 ([Section 7.2](#))

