10.3.4.1 Adverse Events

The Medical Dictionary for Regulatory Activities (MedDRA) dictionary will be used for coding AEs. An AE (classified by preferred term) occurring during the study drug treatment period will

be counted as a treatment emergent AE (TEAE) either if it is not present at Day 1 of this study or if it is present at Day 1 of this study but increased in severity during the treatment period.

The number (percentage) of subjects reporting TEAEs for each preferred term will be tabulated by system-organ class, by system-organ class and severity, and by system-organ class and relationship to study drug. If more than one event occurred with the same preferred term for the same subject, the subject will be counted only once for that preferred term using the most severe or related occurrence for the summary by severity, or relationship to study drug, respectively.

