### **2.7.1 Adverse events (AEs)**

The most recent version of MedDRA before DBL will be used for coding AEs. An AE will be counted as an ORION-8 treatment emergent AE (TEAE) if the AE started on or after ORION-8 baseline or the AE was present prior to ORION-8 baseline but increased in severity on or after

ORION-8 baseline. Since the investigators are required to enter any worsened AE as a separate record, implementation-wise an AE is a TEAE as long as its onset date/time  $\geq$  date/time of ORION-8 baseline.

The following summaries will be presented for ORION-8 TEAEs using number and percentage of subjects with the event:

- Overall Summary of TEAEs
- TEAEs by primary SOC and PT
- TEAEs by PT
- TEAEs by primary SOC, PT, and maximum severity
- TEAEs possibly related to study drug by primary SOC and PT
- Treatment Emergent Serious AEs (TESAEs) by primary SOC and PT
- TESAEs by PT
- TESAEs possibly related to study drug by primary SOC and PT
- TEAEs leading to withdrawal of study treatment by primary SOC and PT
- TEAEs with a fatal outcome by primary SOC and PT

Subject data listings will be presented for AEs with a fatal outcome, SAEs, and AEs leading to drug discontinuation. Those listings will include all AEs in ORION-8 database, regardless of whether they are ORION-8 TEAE.

If more than one event occurred with the same SOC/PT for the same subject, the subject will be counted only once for that SOC/PT, using the most severe occurrence for the summary by severity.

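### A dipstick abnormality already present at Day 1 but first recorded at EOS can be misclassified as treatment-emergent, and the SAP specifies no urinalysis summary that would show it

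*Protocol*

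**What the plan says.** **Recording.** Protocol 7.1.6.4 lists the dipstick fields (among them protein, glucose, ketone, red and white cells) and states: "In case of abnormal results, microscopy and other assessments will be performed at the local laboratory and the abnormality recorded as an AE". The section sets no condition relating the result to Day 1.

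**Timing.** Within ORION-8, Table 6-1 and Sections 6.4 and 6.5 place urinalysis at EOS and not at the dosing visits. A Day 1 reference is nevertheless planned. Section 6.3 lists urinalysis among the feeder EOS procedures that are not repeated, and says: "The same values/samples data will be used for Day 1 assessments in ORION-8 were applicable except for subjects enrolled in Sweden". The assessments replaced in Sweden do not include urinalysis.

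**Definition of a treatment-emergent AE (TEAE).** Under protocol 10.3.4.1 an AE during treatment counts "either if it is not present at Day 1 of this study or if it is present at Day 1 of this study" with an increase in severity during the treatment period. SAP 2.7.1 opens with the same idea: the AE began on or after ORION-8 baseline, or "the AE was present prior to ORION-8 baseline but increased in severity on or after" that point.

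**Implementation.** SAP 2.7.1 then notes that investigators enter a worsened AE as a separate record, and concludes that "implementation-wise an AE is a TEAE as long as its onset date/time" is on or after ORION-8 baseline. Under SAP 5.1.2 an AE with an unknown or partial onset date is a TEAE unless there is enough information to place its start before baseline.

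**Reporting.** The synopsis names urinalysis in the safety endpoint. Protocol 10.3.4.2 says laboratory values will be summarized at each time point. SAP 2.7.3.1 to 2.7.3.4 and Appendix 5.3 cover hematology, coagulation and serum chemistry, but specify no urinalysis summary or criterion. SAP Section 4 declares no change from the protocol-specified analyses.

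**The concern.** The recording rule asks whether a result is abnormal. The TEAE definition asks whether it is new or worse since Day 1. Nothing in either document joins the two. The date-only shortcut is justified for AEs already on record that later worsen, because the worsening gets its own record. That justification does not reach an unchanged finding which becomes an AE for the first time because the EOS dipstick rule requires it.

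The protocol does make this link elsewhere. Section 8.3.2 gives HbA1c-triggered AEs separate rules for subjects with and without a history of diabetes, and uses change from baseline for those with one.

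Safety is a primary objective, the analysis is noncomparative, the population includes people with diabetes, and SAP 2.7.1.1.2 follows renal events. If long-standing glucosuria or proteinuria enters the urinary preferred terms as treatment-emergent, no control arm shows that it is background, and no specified table shows the Day 1 status.

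**Working it through.** No arithmetic applies: the documents give no dipstick abnormality rate, and the point concerns rules. The check is to take the possible histories of an abnormal EOS dipstick and classify each under the protocol definition and under the SAP implementation.

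| History of the finding | Onset as entered | Protocol 10.3.4.1 | SAP 2.7.1 / 5.1.2 |
|---|---|---|---|
| Normal at Day 1, abnormal at EOS | After baseline | TEAE | TEAE |
| Abnormal at Day 1, worse at EOS, entered as a new record | After baseline | TEAE | TEAE |
| Abnormal at Day 1, unchanged, already an ongoing feeder AE | Before baseline | Not TEAE | Not TEAE |
| Abnormal at Day 1, unchanged, first recorded at EOS; site dates it back | Before baseline | Not TEAE | Not TEAE |
| Abnormal at Day 1, unchanged, first recorded at EOS; site enters the test date | EOS | Not TEAE | **TEAE** |
| Abnormal at Day 1, unchanged, first recorded at EOS; onset unknown or partial | Missing in whole or part | Not TEAE | **TEAE by default** |

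The rules disagree only in the last two rows. Three steps lead there.

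1. *The finding must be recorded.* Section 7.1.6.4 requires this for any abnormal result, including one unchanged since Day 1.
2. *It was not already an AE.* Table 6-1 (footnote 12) and Section 6.3 carry ongoing feeder AEs forward. That covers a finding the feeder study recorded as an AE, but not one held only in medical history or only in the feeder laboratory record. The feeder protocols are not supplied, so the split is unknown.
3. *Onset is not placed before baseline.* Neither document tells sites to consult the Day 1 dipstick before dating onset. SAP 5.1.2 could rescue the last row if the Day 1 result were treated as enough information. Its only example, however, is a resolution date before baseline, and no step directs anyone to the urinalysis data.

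The remaining question is whether another output would expose the error. The descriptive laboratory summaries (SAP 2.7.3.1) list the blood panels only. The shift analysis (2.7.3.2) covers eGFR and HbA1c. The clinically significant values (2.7.3.3, Appendix 5.3) and Hy's law (2.7.3.4) use blood parameters. No specified table sets the Day 1 dipstick against the EOS dipstick.

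**The case against.** The strongest reply is that both documents define a TEAE correctly. An abnormality documented at Day 1 has an onset before baseline, and if it is dated that way the SAP rule gives the right answer. No section says that onset is the visit date. On this view the fault is a possible data-entry error, not a planned analysis. Ongoing feeder AEs also carry over, and if the feeder studies used the same recording rule, many such findings would already have a pre-baseline onset. This stands, and it limits the claim to what can happen. It does not remove the point, because the plan gives sites no instruction to look back and gives programmers no check.

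It can also be said that general text (protocol 10.2.1, SAP 2.1) allows any collected data to be summarized or listed, so AEs are not necessarily the only urinalysis output. That is fair. The narrower statement, that the SAP specifies no urinalysis summary, is unaffected.

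Finally, recording every abnormality is an inclusive safety choice, and filtering by clinical significance would be a debatable trade-off. Agreed, and no such filter is proposed. A protocol change would also come late. Enrollment began in April 2019 and 1080 days is 1080/365.25 = 2.96 years, so Day 1080 visits start around spring 2022, before the SAP date of 04-Jul-2022. An amended recording rule would then divide the EOS data into two regimes.

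**Conclusion.** The gap is real but conditional. An unchanged Day 1 abnormality that is first recorded at EOS, with onset entered as the EOS date or left unknown or partial, is classified as treatment-emergent against protocol 10.3.4.1, and no specified summary would show it.

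A reader might infer three stronger things that the documents do not support:

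- *Long-standing abnormalities are counted as new by design.* Both TEAE definitions exclude them unless they worsen. The error arises only through how onset is entered.
- *There is nothing to compare with, because urinalysis is done only at EOS.* The feeder EOS result serves as Day 1.
- *Overall TEAE incidence is inflated by a calculable amount.* No abnormality rate, share already present at Day 1 or onset-dating practice is given. Overall incidence also counts subjects, so someone with any other TEAE adds nothing to it. The effect falls mainly on the urinary preferred terms.

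The size cannot be derived. It depends on site onset dating and on whether the feeder studies recorded abnormal urinalyses as AEs. If they all did, with onset carried forward, the effect could be close to nil. The missing urinalysis summary does not depend on either assumption.

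**What to change.** Make the change in the SAP, before database lock.

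1. In SAP 2.7.3, add a shift table from Day 1 (feeder EOS) to EOS for dipstick parameters such as protein, glucose and blood, for subjects with both results in the database, overall and by feeder treatment group. State how many subjects lack one or both results.
2. In SAP 2.7.1, add that a urinalysis-derived AE is not counted as a TEAE when the Day 1 result shows the same or a worse abnormality, and say how such AEs are identified. Where no Day 1 result is available, keep the present date rule.
3. Through site guidance or data queries, ask sites to check the Day 1 result before assigning onset to an AE raised by the EOS dipstick.

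The recording rule in 7.1.6.4 can stay. The cost is a small amount of programming and some query work, with no new visits or samples. The limitation is coverage: dipsticks are read at the sites and the data specifications are not supplied, so the table reaches only subjects whose two results were captured.

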7.1.6.5 Urine Pregnancy

Urine pregnancy testing will be performed locally at the visits specified in the Schedule of Assessments (Table 6-1), using the supplies provided by the central laboratory.

7.1.6.6 Lipids / Lipoproteins

Lipids and lipoproteins assessments are described in Section 7.2.

7.1.7 Stored samples

The central laboratory will take aliquots of serum and plasma samples from the received routine blood sampling noted above and will store these [REDACTED]

 These samples will be retained on behalf of the Sponsor for a maximum of 1 year following the last subject's last visit in the study. Details regarding the collection, processing, storage, and shipping will be in the Study Laboratory Manual.

7.2 Assessment of Efficacy

Subjects will be in a fasted state for all efficacy laboratory assessments of lipids and lipoproteins. Specimens will be obtained at the time points in the Schedule of Assessments (Table 6-1).

Parameters to be assessed will include:

- Total cholesterol (TC), triglycerides, LDL-C, and high density lipoprotein cholesterol (HDL-C)

8 Adverse Events

8.1 Definitions

8.1.1 Adverse Event

An Adverse Event is any untoward medical occurrence in a patient or clinical study subject administered a medicinal product that does not necessarily have a causal relationship with this treatment. An adverse event can therefore be any unfavorable and unintended sign (eg, an abnormal laboratory finding), symptom, or disease temporally associated with the use of a medicinal product, whether or not considered related to the medicinal product.

8.1.2 Serious Adverse Event

A Serious Adverse Event is any untoward medical occurrence that at any dose:

- Results in death
- Is life-threatening, ie, the subject was, in the opinion of the investigator, at immediate risk of death from the event as it occurred (it does not include an event that, had it occurred in a more severe form, might have caused death)
- Results in a significant, persistent or permanent change, impairment, damage or disruption in the subject's body function/structure, physical activities and/or quality of life
- Requires in-subject hospitalization or prolongs hospitalization
- Is a congenital anomaly/birth defect
- Is another medically significant event where medical and scientific judgement should be exercised in deciding whether other situations should be considered serious reactions, such as important medical events that might not be immediately life threatening or result in death or hospitalization but might jeopardize the patient or might require intervention to prevent one of the other outcomes listed above. Examples of such events are intensive treatment in an emergency room or at home for allergic bronchospasm, blood dyscrasias or convulsions that do not result in hospitalization or development of dependency or abuse. Any suspected

transmission via a medicinal product of an infectious agent is also considered a serious adverse reaction

A distinction should be drawn between serious and severe AEs. Severity is an estimate or measure of the intensity of an AE, while the criteria for serious AEs are indications of adverse subject outcomes for regulatory reporting purposes. A severe AE need not necessarily be considered serious and a serious AE need not be considered severe. For example, nausea that persists for several hours may be considered severe nausea, but not an SAE. On the other hand, a MI that may be considered minor could be an SAE if it prolonged hospitalization.

8.1.3 Special Situations – Adverse Events

There are situations when information is not necessarily considered an adverse event but can possibly contribute to the overall knowledge concerning the safety of the investigational product.

Examples include, but are not limited to, reports of pregnancy/lactation exposures with or without any AEs related to the parent or child; medication errors – actual and potential; accidental exposure; suspected transmission via an investigational product of an infectious agent; drug interaction.

8.2 Collection and Assessment of Adverse Events

8.2.1 Adverse Event Severity

The severity of AEs will be assessed by the investigator using the 3-point scale below:

1 = Mild: Discomfort noticed, but no disruption to daily activity

2 = Moderate: Discomfort sufficient to reduce or affect normal daily activity

3 = Severe: Inability to work or perform normal daily activity

8.2.2 Relationship to Investigational Product

The relationship between the AE and the investigational product will be assessed by using a binary assessment. The investigator should determine whether there is a ‘Reasonable possibility’ or ‘No reasonable possibility’ that the investigational product caused the event based on the definitions below.

Reasonable possibility - There is a reasonable possibility that the administration of the investigational product caused the AE. There is evidence to suggest a causal relationship between the investigational product and the AE

No reasonable possibility - There is no reasonable possibility that the administration of the investigational product caused the AE. There is no temporal relationship between the investigational product and event onset, or an alternative etiology has been established

8.3 Requirements For Additional Safety Data Collection

8.3.1 Special Situations – Additional Safety Data Collection

Special Situations designated for this study include:

- Medication errors that fall into the following categories
 - wrong investigational product
 - wrong dose (including overdose, underdose, change in dosing regimen, strength, form concentration, amount)
 - wrong route of administration
 - wrong subject (ie, not administered to the intended subject)
 - accidental exposure
- Pregnancy/lactation exposures with or without any AEs related to the parent or child
- Suspected transmission via a medicinal product of an infectious agent
- Drug interactions

